### **11.8 Analysis of Safety Data**

Demographic and anthropometric variables will be listed for all subjects in the safety population. Demographic variables will also be tabulated (n, arithmetic mean, median, standard deviation, minimum and maximum of continuous variables, and frequency counts and percentages of categorical variables, as applicable). Subject disposition will also be listed and summarised

Haematology, clinical chemistry and urinalysis values will be listed. For the full blood count, clinical chemistry values and urinalysis, only the abnormal values will be listed and flagged in the listings as "L" (for values lower than the lower limit of the reference range) and "H" (for values higher than the upper limit of the reference range). Clinical chemistry and haematology will be summarised.

Vital signs and ECGs will be listed for all subjects in the safety population.

Adverse events reflecting the System Organ Class (SOC) and preferred term for each AE, concomitant medication reflecting Anatomical-Therapeutic-Chemical classification (ATC) will be listed. Adverse events will be summarised as per the following:

- by treatment
- by treatment, SOC and preferred term
- by treatment, SOC, preferred term time and relationship.
- by treatment, SOC, preferred term and severity.

# **12 ADVERSE EVENTS**

Each subject will be carefully monitored by the investigator for AEs. In addition, information on AEs will be obtained from the subjects by regular questioning of each subject by the study staff, although no leading questions will be asked. When an AE occurs, the investigator will decide whether to withdraw the subject from the study and/or initiate appropriate treatment. After withdrawal from the study, it will be ensured that the subject is given appropriate medical care, if needed, which may take the form of referral to a physician.

In the case of any event requiring medical intervention occurring during the clinic stay, the investigator will institute general supportive measures including, where necessary, respiratory assistance and cardiopulmonary resuscitation.

## **12.2 Definitions**

## **12.2.1** Adverse Events (or Adverse Experiences)

Any untoward medical occurrence in a subject or clinical investigation subject administered a pharmaceutical product and which does not necessarily have a causal relationship with this treatment. It can be any unfavourable and unintended sign (e.g., an abnormal laboratory finding), symptom, or disease temporally associated with the use of an investigational medicinal product.

### 12.2.2 Adverse Drug Reaction

A response to a drug which is noxious and unintended and which occurs at doses normally used in man for prophylaxis, diagnosis or therapy of disease or for modification of physiological function.

### 12.2.3 Unexpected Adverse Drug Reaction

An adverse reaction, the nature or severity of which is not consistent with the SPC (or other applicable product information such as the Investigator's Brochure for the test product). This includes class-related reactions that are mentioned in the SPC but which are not specifically described as occurring with this product.

# 12.2.4 Serious Adverse Events

Serious adverse event (SAE) means an adverse reaction which:

• Results in death;

- Is life-threatening\*
- Requires in-patient hospitalization or
- Prolongation of existing hospitalization
- Results in persistent or significant disability or incapacity, or
- Is a congenital anomaly or birth defect.

Medical and scientific judgment should be exercised in deciding whether other situations should be considered serious reactions, such as important medical events that might not be immediately life-threatening or result in death or hospitalization but might jeopardize the subject or might require intervention to prevent one of the other outcomes listed above. Examples of such events are intensive treatment in an emergency room or at home for allergic bronchospasm, blood dyscrasias or convulsions that do not result in hospitalization or development of dependency or abuse. Any suspected transmission *via* a medicinal product of an infectious agent is also considered a serious adverse reaction.

**Please note** SAEs must be reported within 24 h of knowledge of the event by submitting an initial SAE report via email or fax to *Diamond PV Ltd*:

*Diamond PV Ltd* will notify the Sponsor and Sponsor's Responsible Physician of the SAE via e mail within 24 h of receipt of the initial SAE report.

### 12.3 Classification of Adverse Events

Adverse events have to be recorded on an AE form in the subject's eCRF and graded as mild, moderate, or severe according to the following definitions:

- Mild: Causing no limitation of usual activities; the subject may experience slight discomfort.
- Moderate: Causing some limitation of usual activities, the subject may experience annoying discomfort.
- Severe: Causing inability to carry out usual activities, the subject may experience intolerable discomfort or pain.

\* Life threatening in this context refers to a reaction in which the subject was at risk of death at the time of the reaction; it does not refer to a reaction that hypothetically might have caused death if more severe.

# 12.4 Definition of Adverse Events Relationship.

The investigator will determine the relationship of any adverse event to the IMP according to the following criteria:

- Certain: A clinical event, including laboratory test abnormality, occurring in a plausible time relationship to drug administration and which concurrent disease or other drugs or chemicals cannot explain and response to withdrawal plausible, and reappearance of the reaction on repeated exposure.
- **Probable/Likely:** A clinical event, including laboratory test abnormality, with a reasonable time sequence to administration of the drug, unlikely to be attributed to concurrent disease or other drugs or chemicals and which follows a reasonable response on withdrawal (de-challenge).
- **Possible:** A clinical event, including laboratory test abnormality, with a reasonable time sequence to administration of the drug, but which could also be explained by concurrent disease or other drugs or chemicals. Information on drug withdrawal may be lacking or unclear.
- Unlikely: A clinical event, including laboratory test abnormality, with a temporal relationship to drug administration which makes a causal relationship improbable and in which other drugs, chemicals or underlying disease provide plausible explanation.
- Not related: A clinical event, including laboratory test abnormality, which can be explained by any reason excluding the administered drug.
- **Conditional/Unclassified:** A clinical event, including laboratory test abnormality, which can / cannot be judged because more data for proper assessment needed or additional data under examination.
- Not assessable/Unclassified: A report suggesting an adverse event that cannot be judged because information is insufficient or contradictory, and which cannot be supplemented or verified.

# 12.5 Adverse Events Documentation

The recording of every single AE/ SAE has to be in line with ICH Topic E2B (M) and has to meet the following requirements:

- Detailed subject data
- Exact documentation of the event
- Exact description of temporal sequence to the therapy course
- Documentation of severity

- Documentation of the results of diagnostic and therapeutic measurements
- Results of a repeated exposure (re-exposure) if possible
- Details of the development and outcome including medical judgment
- As much data as possible have to be obtained which are important for judgment concerning the relationship of the AE/SAE to IMP
- Critical examination of the relationship to IMP.

All AEs have to be charted according to this scheme when spontaneously reported by the subject, observed by the principal investigator or designee or elicited by general questioning.

# 12.6 Reporting Procedures of Adverse Events/Serious Adverse Events

The principal investigator or designee is responsible for recording in the eCRF **all** AEs which have occurred during the study (including clinically important deviations of laboratory values from the reference ranges), regardless of their relationship to the IMP. Any AE or SAE reported to site by the subject after the end of the study within a reasonable time period and considered to have been caused by the IMP must also be recorded. All recorded AEs will be summarised and reported on in the clinical study report.

All suspected adverse reactions that occur in the concerned study, and that are both unexpected and serious are subject to expedited reporting. A suspected unexpected serious adverse reaction (SUSAR) which is fatal or life-threatening will be reported as soon as possible to the authority.

Occurrence of **any** SAEs (including death, irrespective of the reason) has to be notified **immediately** (within 24 hours) after becoming aware of the event, to the monitor, sponsor, and the Competent Authority (where appropriate i.e. a SUSAR). The notification must be followed by a written report within 48 hours of the initial notification, or at latest on the following working day. The first report should contain a detailed description of the observed symptoms and the concomitant therapy. The investigator has to judge the possible causal relationship between the event and the IMP and should arrange additional examinations at his/her discretion to clarify if the event is connected with the IMP. He/She should consult a specialist if necessary.

All AEs and SAEs have to be followed up until an outcome is known. In the event of an SAE, the outcome has to be reported in the eCRF and to the principal investigator, sponsor, monitor, the REC and the Competent Authority (where appropriate i.e. a SUSAR).

# 12.7 Pregnancy

Pregnancies must be reported to Diamond PV Ltd immediately (within 24 hours) and should be followed up to determine outcome, including spontaneous or voluntary termination, details of the

birth, and the presence or absence of any birth defects, congenital abnormalities, or maternal and/or new-born complications.

Pregnancy outcomes must be collected for all female volunteers and the female partners of any males who took the IMP. Consent to report information regarding these pregnancy outcomes should be obtained from the mother.

## 13 LEGAL AND ADMINISTRATIVE ASPECTS

### **13.2 Documentation**

The Investigator site file and associated study documentation will be archived for at least 5 years after the end of the study (last subject last visit) as per The Medicines for Human Use (Clinical Trials) Amendment Regulations 2006 (No. 1928) The study documentation may be transferred to an offsite storage facility during this period but will remain under the control of MEU.

The Sponsor has delegated the set up and maintenance of the Sponsor trial master file (TMF) to MEU. The TMF will checked by the Sponsor's monitor at monitoring visits and will be returned to the Sponsor at the end of the study, who will archive it for at least 25 years after the end of the study.

### **13.3 Publication of Results**

If a publication based on the results of this study is envisaged, approval from the sponsor will be obtained and a draft manuscript will be submitted to the sponsor for scrutiny and comment. The choice of scientific journal will be mutually agreed on by the principal investigator and the sponsor.

#### **13.4 Sponsor's Obligation**

The onus rests with the sponsor to ensure that this clinical study protocol complies with all their requirements.

### **13.5 Clinical Study Report**

An integrated clinical study report (CSR) will be prepared in accordance with the standards of the ICH Guideline for Structure and Content of Clinical Study Reports (ICH E3). The CSR will be signed by the investigator in accordance with Annex I of the Directive 2001/83/EC as amended. Copies will be provided to the REC in accordance with regulatory requirements and MEU SOPs. In the event of premature termination of the study or other conditions specified in ICH E3, an abbreviated CSR may be prepared.

| λ _z | Terminal Elimination Rate Constant |
| LLOQ | Lower Limit of Quantification |
| MedDRA | Medical Dictionary for Regulatory Activities |
| PK | Pharmacokinetic |
| PT | Preferred Term |
| SAF | Safety Analysis Set |
| SAP | Statistical Analysis Plan |
| SD | Standard Deviation |
| SOC | System Organ Class |
| t _½ | Terminal Elimination Half-Life |
| TEAE | Treatment Emergent Adverse Event |
| t _{max} | Time of the Maximum Observed Plasma Concentration |
| WHO Drug | World Health Organization Drug Dictionary |

1 INTRODUCTION

This document details the statistical analysis that will be performed for the Nova Laboratories study: A single centre, single dose, open-label, randomised, two period crossover study to assess the bioequivalence of an oral azathioprine suspension 10mg/mL (Jayempi™) versus oral azathioprine tablet 50mg (Imurek®, Aspen Pharma Trading Limited, Dublin, Ireland) in at least 30 healthy adult subjects under fasting conditions.

The proposed analysis is based on the contents of the Final Version of the protocol (dated 03-May-2019). In the event of future amendments to the protocol, this statistical analysis plan (SAP) may be modified to account for changes relevant to the statistical analysis.

The table, listing and figure shells are supplied in a separate document.

2 STUDY OBJECTIVES AND DESIGN

2.1 Study Objectives

The primary objective of the study is to assess whether Nova's oral azathioprine suspension (Jayempi™) and a marketed azathioprine tablet formulation (Imurek®) are bioequivalent.

The secondary objectives of the study are

- To assess the safety and tolerability of the test product, azathioprine oral 10mg/mL suspension
- To determine the plasma concentrations and pharmacokinetics of the metabolite mercaptopurine

2.2 Study Endpoints

The primary endpoints of the study are

- Maximum observed plasma concentration (C_{max})
- Area under the plasma concentration curve from zero to time of the last quantifiable concentration (AUC_{0-t})
- Area under the plasma concentration curve from zero extrapolated to infinity ($AUC_{0-\infty}$)

The secondary endpoint(s) are

- Time to maximum observed plasma concentration (t_{max})
- Terminal elimination rate constant (λ_z)
- Apparent terminal elimination half-life ($t_{1/2}$)

2.3 Study Design

This will be a single-dose, open-label, randomised, two-period crossover study with orally administered 1 x 5mL (50mg) of Jayempi™ Oral Suspension 10mg/mL versus oral azathioprine tablet 50mg (Imurek®, Aspen Pharma Trading Limited, Dublin,

Ireland) on two separate occasions conducted under fasting conditions in healthy male and female subjects at a single study centre.

The study will comprise:

- Thiopurine methyltransferase (TPMT) testing
- Screening period of maximum 28 days
- Two treatment periods (each of which will include a PK profile period of 12 hours) separated by a wash-out period of at least 3 calendar days (minimum number of days based on half-life of the analyte) and maximum of 14 calendar days between consecutive administrations of the IMP
- A post-study visit 7-10 days after the last dose of the last treatment period of the study

Subjects will be randomly assigned to treatment sequence, prior to the first administration of IMP.

2.4 Visit Structure

The visit structure and scheduled assessments are detailed in protocol section 7.1.3.

3 SAMPLE SIZE

Thirty (30) subjects will be randomised, to allow for dropouts or subjects who otherwise fail to complete the study with at least 28 evaluable subjects. The sample size for this study has been selected without any formal statistical considerations. However, similar bioequivalence studies

- AT/H/0270/001-002/DC
- UK/H/2846/004/DC
- UK/H/934/01/DC

for azathioprine have recruited between 24-30 subjects. This figure has been determined adequate to meet the study objectives.

4 RANDOMISATION

The randomisation will be produced by SQN. The treatment will be allocated by staff at the site using the randomisation list provided.

Subjects who withdraw or are withdrawn from the study may be replaced (recruitment continued), if fewer complete the study than the estimated number of evaluable subjects. Replacements will be randomised to treatment (they will not necessarily be on the same treatment sequence).

5 INTERIM ANALYSIS

No interim analysis is planned for this study.

6 ANALYSIS PLAN

6.1 General

Summary statistics for continuous variables will consist of number of non-missing observations (n), arithmetic mean, standard deviation (SD), minimum, median and maximum, unless specified otherwise. The precision of these variables is defined in the table, figure and listing shells document.

For categorical variables the number and percentage of subjects in each category will be presented, based on the number of subjects in the analysis set, unless otherwise specified.

6.2 General Derivations

This section provides details of general derivations. Derivations specific to the parameter of interest are detailed within the specific SAP section.

- Definition of baseline

A within-period baseline is defined as the last non-missing value (including scheduled and unscheduled assessments) recorded prior to the subject receiving the respective study treatments for the respective period.

- Incomplete dates

For calculation purposes, incomplete dates will be completed using worst case. Further details are detailed in the relevant sections as required.

- Non-numeric values

In the case where a variable is recorded as "> x", "≥ x", "< x" or "≤ x", then for analysis purposes a value of x will be taken. Where a range of values is quoted the midpoint of the range will be taken.

6.3 Analysis Sets

The **Enrolled set** includes all subjects who provide informed consent irrespective of whether they were randomised or received study treatment.

The **Safety analysis set (SAF)** consists of all subjects who take at least one administration of study treatment. Subjects will be analysed according to the treatment actually taken.

The **Pharmacokinetic (PK) set** will consist of all subjects who complete the study and for whom primary PK variables can be calculated for all treatments.

In case of events such as vomiting, diarrhoea and use of concomitant medication, which could render the plasma concentration time profile unreliable, such subjects may be excluded from the PK population after review of the severity of the event and the start and stop time in relation to dosing. When vomiting occurs within 2x the calculated median t_{max} of the reference (tablet) product, data from all treatments being compared will be excluded from PK and statistical evaluation. Subjects with pre-dose azathioprine concentrations $\geq 5\%$ of C_{max} will be excluded from all statistical PK analysis (including descriptive statistics). The available concentration data of the

above subjects and those who do not complete the study will only be listed, not presented in descriptive statistics or included in PK or formal statistical analysis.

The list of subjects included in the PK will be agreed prior to database lock once all study data is available. The definitions for the enrolled set and SAF are sufficient to determine the subjects included within these analysis sets and so do not require listing and agreeing prior to database lock.

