#### 7.2.4 Post-study Evaluations

See Table 7-1.

If a subject is withdrawn or chooses to withdraw from the study, the investigator will make every effort to perform all evaluations described for the post-study visit.

Post study laboratory investigations with variables outside the reference ranges will not necessarily be repeated to establish if and when those variables returned to within the reference ranges. The variables will be reviewed against the clinical background, other relevant investigations and their relevance to the administered IMP, before a decision will be taken to repeat the investigations in question. At the discretion of the investigator, the investigations of certain variables outside the reference ranges may be repeated until the variables return to within the reference range for the particular laboratory test, or until the investigator considers the repeated variable to be at an acceptable level in relation to the reference range. If the investigator has made every effort to contact the subject and the subject remains unavailable to attend the clinic for repeat of applicable laboratory investigations, the investigator may declare the subject lost to follow-up.

In cases where results of post-study evaluations are reported after the database has been locked, the applicable clinical laboratory reports will be presented in the appendices to the clinical study report.

All evaluations described for the post-study visit will be performed on all subjects who completed the study.

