# 7.3.2 Exclusion Criteria

- 1. Evidence of psychiatric disorder, antagonistic personality, poor motivation, emotional or intellectual problems likely to limit the validity of consent to participate in the study or limit the ability to comply with protocol requirements.
- Current alcohol use > 21 units of alcohol per week for males and >14 units of alcohol per week for females.
- 3. Regular exposure to substances of abuse (other than alcohol) within the past year.
- 4. Use of any medication, prescribed or over-the-counter or herbal remedies, within 2 weeks prior to the first administration of IMP except if this will not affect the outcome of the study in the opinion of the investigator.
- 5. Participation in a new chemical entity clinical study within the previous 3 months or a marketed drug clinical study within the 30 days before first dose of IMP and until the study is complete (i.e. the subject has undergone their post study visit). (*Washout period between studies is defined as the period of time elapsed between the last dose of the previous study and the first dose of the next study*).
- 6. A major illness during the 3 months before commencement of the screening period.

- 7. History of hypersensitivity or allergy to the IMP or its excipients or any related medication (please refer to azathioprine Oral suspension IMPD and Imurek® SmPC for list of excipients).
- 8. History of bronchial asthma or any other bronchospastic disease, history of epilepsy, history of porphyria, history of rheumatoid arthritis, history of pancreatitis, history of any liver disease or any other medical condition that in the opinion of the investigator may interfere with the study outcome measures or impact upon the safety of the subject.
- 9. Clinically relevant abnormalities in the coagulation status.
- 10. Clinically diagnosed peptic ulceration within the past 5 years.
- 11. History of bleeding disorders.
- 12. History of any of the following: seizures, diabetes, migraine, cardiovascular (including hypertension and hypotension), pulmonary, neurological, hepatic, renal or gastrointestinal conditions, hematopoietic abnormalities, blood disorders, gout, leg ulcers, lactose intolerance or ongoing infectious diseases at the discretion of the investigator.
- 13. Subjects with a deficient, low or intermediate TPMT enzyme activity by means of phenotyping.

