# **11.2.1 Pharmacokinetic Population**

All subjects who complete the study and for whom primary PK variables can be calculated for all treatments will be included in the statistical PK analysis for the study.

In case of events such as vomiting, diarrhoea and use of concomitant medication, which could render the plasma concentration-time profile unreliable, such subjects may be excluded from the PK population after review of the severity of the event and the start and stop time in relation to dosing. When vomiting occurs within 2x the calculated median  $t_{max}$  of the reference product, data from all treatments being compared will be excluded from PK and statistical evaluation. Subjects with pre-dose azathioprine concentrations  $\geq 5\%$  of  $C_{max}$  will be excluded from all statistical PK analysis (including descriptive statistics). The available concentration data of the above subjects and those who do not complete the study will only be listed, not presented in descriptive statistics or included in PK or formal statistical analysis.

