# **11.5.1 Primary Variables**

- Maximum observed plasma concentration (Cmax)
- AUC Area under the plasma concentration curve from zero to time of the last quantifiable concentration (AUC0-t)
- Area under the plasma concentration curve from zero extrapolated to infinity  $(AUC_{0-\infty})$ .

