6.4 Data presentations

The data will be summarised in tabular form by treatment group ('Oral azathioprine tablet 50mg' and 'Oral azathioprine suspension 10mg/mL' with the following exceptions: disposition of subjects, background and demographic characteristics which will be summarised by treatment sequence ('Oral azathioprine tablet 50mg – Oral azathioprine suspension 10mg/mL' and 'Oral azathioprine suspension 10mg/mL – Oral azathioprine tablet 50mg') and overall subjects ('Overall') treatment group.

Only scheduled post-baseline laboratory, vital signs and ECG values will be tabulated, post-baseline repeat/unscheduled assessments will be disregarded, although they will be listed and in particular all clinically significant values will be noted.

Analysis sets, protocol deviations and eligibility listing will be summarised using the enrolled set, PK outputs will be summarised using the PK set and everything else will be summarised using the SAF.

Listings will be sorted by treatment sequence, subject number and date/time of assessment.

Graphical presentations of the data will also be provided where appropriate.

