6.5 Disposition of subjects

The number and percentage of all subjects enrolled, included in the SAF, PK analysis set, who completed the study and prematurely discontinued the study, who completed study treatment and prematurely discontinued study treatment, study duration and treatment duration, will be summarised. The number and percentage of subjects will be summarised by their reasons for withdrawal from the study.

Study duration will be derived as the number of days between first visit and the date of study completion or the date of early study withdrawal. Treatment duration will be derived as the number of days between first administration of study treatment in period 1 and date of study completion or the date of early study withdrawal.

Eligibility for each of the analysis sets along with reasons for exclusion will be listed. Study completion/withdrawal data will be listed.

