6.10 Pharmacokinetics

Summary statistics for PK outputs will be reported using n, arithmetic mean, geometric mean, median, coefficient of variation, standard deviation, minimum and maximum.

For purposes of analysis, the test product is Jayempi 50mg/mL (azathioprine oral suspension) and the reference is Imurek 50mg (oral azathioprine tablet).

Plasma concentrations of azathioprine (both oral and tablet) will be listed and summarised over time. Concentrations below the lower limit of quantification (LLOQ) of 0.2ng/ml will be indicated as below the lower limit of quantification (BLQ). For PK summaries and analyses, BLQ concentrations will be handled as follows:

- All BLQ values in the absorption phase, prior to the first reported concentration, will be substituted by zeros.
- The BLQ values between evaluable concentrations will be substituted by $0.5 \times$ LLOQ, before the calculation of the PK variables.
- Terminal BLQ values will be set to missing.

These measures are taken to prevent an over-estimation of AUC. Values reported as 'NS' (no sample) will be set to "missing".

For the purposes of PK analysis, missing concentrations will be deleted, resulting in an interpolation between the nearest two concentration values. A table reflecting summary statistics per product will be provided for PK variables of azathioprine, including the number of points used to calculate λ_z (λ_z will, however, not be summarised).

A table reflecting summary statistics will be provided for the ratios (%test/reference) of the primary PK variables (C_{max} , AUC_{0-T} and $AUC_{0-\infty}$), for $t_{1/2}$ and for the difference (test – reference) of t_{max} .

Analysis of t_{max} will be done using Wilcoxon's Signed Rank test. The median t_{max} of the test and reference will be tabulated together with the p-value from Wilcoxon's Test.

The test product (azathioprine only) will be compared to the reference product by means of statistical analysis with respect to the primary PK variables (C_{max} , AUC_{0-T} and $AUC_{0-\infty}$) using an analysis of variance (ANOVA) with sequence, subject(sequence), product and period effects after logarithmic transformation of the data. Point estimates and 90% confidence intervals for the "test/reference" geometric mean ratios of these variables will be tabulated.

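### Read literally, the single PK set drops a subject's valid Cmax and AUC0-t pairs when only AUC0-inf cannot be calculated in one period (low-priority improvement)

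*SAP*

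**What the plan says.** SAP 6.3 (Analysis Sets) says that the PK set "will consist of all subjects who complete the study and for whom primary PK variables can be calculated for all treatments". Protocol 11.2.1 (Pharmacokinetic Population) agrees: "All subjects who complete the study and for whom primary PK variables can be calculated for all treatments will be included".

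Protocol 11.5.1 and SAP 2.2 name the same three primary variables: Cmax, AUC0-t and AUC0-inf. The last is described as "Area under the plasma concentration curve from zero extrapolated to infinity".

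SAP 6.4 (Data presentations) ties the outputs to that one set: "PK outputs will be summarised using the PK set". SAP 6.10 fits, for each primary variable, a log-scale ANOVA with sequence, subject within sequence, product and period. Bioequivalence is judged on the 90% confidence intervals against 80.00% to 125.00%.

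SAP 6.3 also has the list of subjects in the PK set agreed before database lock, and SAP 6.5 has reasons for exclusion from each set listed.

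**The concern.** Cmax and AUC0-t are read directly from the observed profile. AUC0-inf also needs an estimate of the terminal slope, so it can fail in a profile where the other two are sound. SAP 6.10 shows one route: terminal values below the quantification limit are set to missing, which may leave too few points for a slope. Neither document says when the slope or AUC0-inf counts as calculable.

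Because membership is decided once per subject, that failure would also take the subject out of the Cmax and AUC0-t analyses. Data already collected on two of the three variables that decide the trial would be left out of their own intervals because a third variable is missing. The sample size has no formal statistical basis (Protocol 11.3, SAP 3), so no stated power margin is available to absorb an avoidable loss.

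**Working it through.** **Tracing the rule**

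1. Membership is per subject and depends on the primary PK variables being calculable for both treatments (SAP 6.3, Protocol 11.2.1).
2. AUC0-inf is one of those variables (SAP 2.2, Protocol 11.5.1).
3. All PK outputs use that set (SAP 6.4).
4. A subject without AUC0-inf in one period therefore fails the membership test and leaves all three ANOVAs.
5. Neither document gives a set per variable, an at-least-one-variable rule or an exception for AUC0-inf.
6. The replacement rule (Protocol 7.3.4 and 8.4, SAP 4) covers subjects who withdraw or are withdrawn. It does not cover someone who finishes both periods but lacks AUC0-inf.

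**The plan's own figure**

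The plan randomises 30 to keep at least 28 evaluable. It gives no CV, expected ratio or power, so the number cannot be re-derived. The only arithmetic link is 28/30 = 93.3% retention.

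**Interval width**

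For a balanced two-period crossover the log-scale 90% CI half-width is s_w × t(0.95, n−2) × √(2/n). The within-subject SD s_w cancels from ratios of widths.

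| n | t × √(2/n) | Relative to n = 28 |
|---|---|---|
| 28 | 0.4558 | 1 |
| 27 | 0.4649 | 1.020 |
| 26 | 0.4745 | 1.041 |

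With exact sequence splits the factor is t × √((1/n1 + 1/n2)/2). It is 0.4652 for 13/14 and 0.4759 for 12/14, so the ratios are 1.021 and 1.044.

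Illustration at an assumed CV of 25% (s_w = √ln(1.0625) = 0.2462) and an observed ratio of 0.95:

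- n = 28: 84.91% to 106.28%
- n = 27: 84.72% to 106.52%
- n = 26: 84.52% to 106.77%

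**How many subjects might be lost**

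The failure rate p per profile is an assumption. If failures are independent between periods, a subject is lost with probability 1 − (1 − p)².

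| Assumed p | Subject lost | Expected of 28 |
|---|---|---|
| 1% | 1.99% | 0.56 |
| 2% | 3.96% | 1.11 |
| 5% | 9.75% | 2.73 |
| 10% | 19.0% | 5.32 |

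**Joint power**

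This was simulated with 400,000 balanced crossovers per scenario, n = 28 and a true ratio of 0.95. Success means that all three 90% CIs lie within 80.00% to 125.00%. Assumed within-subject log-scale correlations are 0.95 between the two AUCs and 0.6 between Cmax and each AUC. AUC0-inf is missing completely at random. Entries are power (%) with the single set, then with per-variable inclusion.

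| Assumed CVs | One missing | Two missing |
|---|---|---|
| All 15% | 98.54 / 98.71 | 98.19 / 98.56 |
| All 20% | 86.42 / 87.23 | 84.82 / 86.37 |
| Cmax 20%, AUC 25% | 72.87 / 73.47 | 70.75 / 71.94 |
| All 25% | 65.53 / 66.70 | 63.05 / 65.38 |
| Cmax 30%, AUC 20% | 60.60 / 62.57 | 58.14 / 62.21 |
| All 30% | 42.64 / 43.89 | 39.69 / 42.31 |

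The gain runs from 0.17 to 4.07 points. It is limited because AUC0-inf keeps the smaller n either way.

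**The case against.** **The wording can be read more leniently.** The word all qualifies the treatments, not the variables, so a variable-by-variable reading is possible. The listing-only sentence in SAP 6.3 closes a paragraph on vomiting, unreliable profiles and pre-dose concentrations, and does not clearly reach a completer who lacks only AUC0-inf. The SAP also treats the PK list as something to be agreed before lock, unlike the enrolled and safety sets. This stands in part: exclusion is what the text implies, but it is not certain to happen. The agreement step makes an exclusion visible and adds no criterion that would prevent it.

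**The trigger may never occur.** Six samples are scheduled from 3 to 12 hours, and Protocol 5.2 gives azathioprine a half-life of 3 to 5 hours, so sampling spans 12/5 = 2.4 to 12/3 = 4 half-lives. No acceptance rule disqualifies an AUC0-inf that the software returns. This stands: nothing suggests that failures would be common.

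**The buffer may cover it.** Counted from 30 full profiles, one or two losses leave 29 or 28, which still meets the plan. This also stands, although the same buffer must cover drop-outs and the other exclusions, and the relative widening is similar (about 1.8% and 3.8%).

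**One common set is coherent.** Using the same subjects for three variables that are judged together is a legitimate choice, prespecified identically in both documents. That is the real trade-off of the change.

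**Stronger readings that the documents do not support.** A reader might infer that the completion requirement would also exclude subjects with two full profiles who miss the post-study visit. No passage says so. Protocol 7.2.4 speaks of post-study evaluations for subjects who have already completed, and the exclusion criterion that mentions the post-study visit concerns participation in other studies. A reader might also infer that n would be missing from the bioequivalence table. The table shells are in a separate document, so this cannot be judged here.

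**Conclusion.** The point holds as a matter of wording. Read literally, one uncalculable AUC0-inf costs a subject's Cmax and AUC0-t pairs as well, and no text prevents it.

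The consequence is modest and conditional. From 28 subjects, one or two such losses widen the Cmax and AUC0-t intervals by about 2% or 4% on the log scale. That result needs no CV, only the assumed number of losses. The joint-power gain of roughly 0.2 to 4 points rests on assumed CVs, correlations and failure counts, and its top end needs two failures together with a Cmax CV of 30% and an AUC CV of 20%. If AUC0-inf can be calculated in every profile, the effect is zero.

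A reader might go further and infer a biased comparison or a trial that cannot meet its aim. The documents support neither: they give no failure rate, no CV and no link between failure and product. This is a low-priority improvement, worth making because it is cheap.

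**What to change.** In SAP 6.3 and Protocol 11.2.1, define inclusion by variable: a subject enters the ANOVA for a primary variable when that variable can be calculated in both treatment periods. A subject without AUC0-inf in one period then leaves only the AUC0-inf analysis. Leave the exclusions for vomiting, unreliable profiles and pre-dose concentrations unchanged.

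Change both documents together, because their rules now match and SAP 6.19 declares no departure from the protocol. Settle the wording before the PK list is agreed ahead of database lock.

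The cost is a few words in two sections, with no new data or procedures. The downside is that n may differ between the three primary variables, so they may no longer share one common set of subjects.
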